
In order to avoid imparting biases regarding which treatment is the 'intervention' and which the 'control', AcTIVE-CBT is referred to as 'extended CBT' in the Informed Consent documents and all discussions with the patient, and TBSCE treatment is referred to as 'brief CBT' in the Informed Consent documents and all discussions with the participant.

The AcTIVE CBT and TBSCE control conditions will both be delivered by licensed Clinical Psychologists with specific expertise in cognitive-behavioral therapy and its application to the treatment of chronic pain. Both treating psychologists have appointments within Rehabilitation Care Services at VAPSHCS and are approved for clinical telehealth service modalities. Both study psychologists will be instructed by [name] in the aspects of clinical CBT treatment to be provided for participants in this study, but are considered clinical staff providing standard-of-care clinical services for chronic pain, and thus not actively engaged in the research procedures. Participants receiving a given treatment (AcTIVE CBT or TBSCE) will generally receive the same information; however, we expect some variation in the amount of time spent on each topic and the specific language used to convey materials. As per usual clinical practice, psychologists will tailor the information in whatever way is indicated to ensure understanding of the content, and to provide individualized support based on personalized goals, barriers, and abilities. If patients specifically request to have one or more in-person sessions of either AcTIVE-CBT or TBSCE in lieu of video telehealth or telephone (respectively), therapists will accommodate such requests as their clinical schedules and availability allow.

ACTIVE-CBT

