7. It is not possible to blind patients and rehabilitation psychologists to whether or not they are receiving AcTIVE-CBT or TBSCE. To limit the potential for influencing participants' perceptions of the interventions as more or less likely to be effective, participants will not be specifically told which of the AcTIVE-CBT or TBSCE treatments represents the intervention of interest or the control treatment in the current study. They will however have full advance knowledge of what the treatments will actually entail.

Table 2: Blinding Status of Research Staff		
	Blinded/Unblinded and Reason	When blinded
[name] (PI)	Not blinded (main study physician responsible for clinical issues)	N/A
[name]	Not blinded (study physician responsible for clinical issues pertaining to mental health)	N/A
Drs. [name], [name], [name]	Yes; blinded when not acting as the 2 nd interventional spine attending physician (which he/she will be in cases when another spine provider is the treating interventional spine provider ^a)	Entire study, see superscript 'a' to the left
[name]	Not blinded; except when he is acting as the treating interventional spine provider (in which instances he will be blinded ^b)	Entire study⁵
[name]	Blinded and no contact with individual-level study data at any point	Entire study

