uncertainty about the true effectiveness of targeted steroid injections, similar to the situation with LRFA effectiveness. The risks of the LRFA procedure will be discussed, including that it entails applying heat to a nerve that supplies the facet joint (which destroys the nerve at least temporarily) and applying anesthetic around the nerve to the facet joint. Risks will be noted, including infection, bleeding, nerve damage, pain at the injection site, allergic reaction, and worsening of back pain. The risks of the simulated LRFA control procedure with targeted steroid injections will also be discussed, which generally involve the same possible risks as LRFA, but with a lower expected frequency of such risks since the nerves are not destroyed. Patients will be informed that, if they meet all inclusion criteria and are ultimately randomized, they will have a 50% chance (1:1 randomization) that they will not receive LRFA initially, but will receive simulated LRFA with targeted steroid injections instead. Potential risks of enrolling in the trial and being randomized to the control procedure will be discussed, including the trial and being randomized to the control procedure will be discussed, including the possibility that they may continue to experience back pain. Potential benefits of enrolling in the trial and being randomized to the control procedure will be discussed, including the possibility that the patient may have back pain improvement and avoid the need for LRFA, surgery or other interventions for pain and that closer follow-up than usual will be given.

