Study staff will also describe to potential participants that many behavioral treatments for CLBP are available, and some (such as CBT) have evidence of effectiveness. However, we don't know what components of CBT-related treatments create these positive effects. We will explain moreover that CBT, even video-based CBT such as the AcTIVE-CBT intervention, consumes substantial Veteran time which may not result in any effects beyond those of the initial education, the provision of written materials, and the formal structure needed for a patient-directed graded, progressive, education and self-management program. Therefore, this study involves comparing two programs of CBT which are delivered by telehealth methods, intended to make it easier for Veterans to access CBT, without the burdens of travel and transportation to repeated face-to-face appointments. One program is an 'extended CBT' program, which involves a program requiring more appointments and video-based sessions with a psychologist (ACTIVE-CBT). The other program is a 'brief CBT' program, which involves a single telephone-based session with a psychologist, and a structured program for education and for the patient to apply the concepts of CBT independently and at their own pace, using formal written materials, with subsequent check-ins by the psychologist as needed (TBSCE). Patients will be informed that, if they meet all inclusion criteria and are ultimately randomized, they will also have a 50% chance (1:1 randomization) of receiving one of these 2 treatments. The extended CBT treatment (AcTIVE-CBT) will involve eight 1-hour video sessions with a psychologist and the provision of educational materials; and the brief CBT treatment (TBSCE) will involve one 1-hour telephone session with a psychologist and the provision of educational materials, with one follow-up phone call by the psychologists approximately 1-2 months after the 1st session of TBSCE, and focused troubleshooting with any problems that might arise. Both treatments will involve the patient needing to wear a Fitbit activity tracker daily for 3 months. However, the AcTIVE-CBT treatment will involve specific therapyrelated interactions surrounding the Fitbit unit. Participants in the AcTIVE-CBT group will be given a 'pledge' form which indicates their intent to try to upload their information to the Fitbit website regularly and consult their Fitbit regularly during the study, to the extent that they are able (Attachment O -Pledge Visit 2 Extended). Participants in the TBSCE group will be given a 'pledge' form which indicates their intent to try to upload their information to the Fitbit website regularly, but will not include prompts for participants to consult their Fitbit during the study, and will ask them not to spend time reviewing their information on the Fitbit website or using the Group or Friend functions, to the extent that they are able, during the first 3 months of the study (Attachment N – Pledge Visit 2 Brief). At the conclusion of the study, unless participants elect not to do so, participants will be provided with an official report containing their study data, including their activity tracker data. Participants may keep the Fitbit unit/s that they use during the study, after study conclusion, irrespective of their group assignment.

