
In addition, patient consent will include that the study will follow participants for 3 months and collect information on back specific functional status, pain, Fitbit data, health-related quality of life, and other study measures. Potential participants will consent either to data collection for 3 months only, or to also include an ongoing data collection on a monthly basis after the 3-month assessment, for up to 9 additional months, or until the funding period ends (whichever date comes first). Participants may change their mind about the duration of time they wish to participate in data collection at any time during the study.

Potential participants will be informed that, if they choose to participate in the study, they will remain blinded to which study interventional procedure they received (LRFA vs. simulated LRFA) until 3 months. Pledge forms will ask participants to not actively seek out to find answers for which procedural group they are in. At 3 months they will have the opportunity to become unblinded if they wish, and make any usual health care decisions related to CLBP that they wish at that time, with or without the input of their treating physician. This might include having LRFA, irrespective of whether they had already received LRFA or simulated LRFA as part of this study. They will also be informed that if they wish to become unblinded at any time during the study (to seek treatment off protocol for example) or discontinue enrollment in the trial, they can do so. Potential participants will also be told that at 3 months they can be informed about which of the 2 behavioral interventions (AcTIVE-CBT and TBSCE) constituted the official study 'control'. At 3 months they will have the opportunity to become unblinded to this information if they wish, and make any usual health care decisions related to CLBP that they wish at that time, with or without the input of their treating physician. This might include other behavioral treatments including conventional in-person CBT, typical video-based telehealth as offered by the VAPSHCS TREWI program, or others, irrespective of whether they received the AcTIVE-CBT or TBSCE treatment as part of this study. They will also be informed that if they wish to become unblinded at any time (and to pursue usual care outside of the study protocol) or discontinue enrollment in the trial, they will be allowed to do so at their discretion.

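### The consent discussion names AcTIVE-CBT when doubting added benefit and gives no matching caution about brief CBT, which weakens the neutral presentation this unblinded comparison relies on

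*Combined protocol and SAP*

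**What the plan says.** Section 5.1 (Blinding Strategy, item 7) states that neither patients nor psychologists can be blinded to AcTIVE-CBT versus TBSCE. Its substitute is restraint in presentation: "To limit the potential for influencing participants' perceptions of the interventions as more or less likely to be effective", participants are not told which CBT is of interest and which is the comparator, although they know in full what each involves. The description of the CBT treatments in the same section adds the labels 'extended CBT' and 'brief CBT', with the aim "In order to avoid imparting biases regarding which treatment is the 'intervention' and which the 'control".

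Section 5.3 (Detailed Description of Informed Consent) sets out what staff tell candidates:

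- On CBT generally, some behavioral treatments have evidence of effectiveness, but "we don't know what components of CBT-related treatments create these positive effects".
- On the longer program, candidates hear that such treatment "consumes substantial Veteran time which may not result in any effects beyond those of the initial education, the provision of written materials", plus a framework for self-directed work. The subject of that sentence is worded broadly, as "CBT, even video-based CBT such as the AcTIVE-CBT intervention".
- On the shorter program, a practical description: "The other program is a 'brief CBT' program, which involves a single telephone-based session with a psychologist", followed by structured education, self-paced application, written materials and check-ins as needed.
- On the procedures, debate about LRFA's effectiveness is described, and candidates then hear of "uncertainty about the true effectiveness of targeted steroid injections, similar to the situation with LRFA effectiveness".
- On unblinding, candidates hear that at 3 months they can learn "which of the 2 behavioral interventions (AcTIVE-CBT and TBSCE) constituted the official study 'control".

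Section 5.5 says that all main outcomes except Fitbit step counts are patient-reported. Section 5.6 says that the purpose is to learn effect sizes and variability for a definitive trial.

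**The concern.** In the CBT comparison the participant knows the treatment received and also scores the primary outcome, the RMDQ. The only protection against expectation effects is that candidates should not be led to think one program more likely to work than the other. If the consent discussion suggests that the longer program may add nothing to what the shorter one contains, and says nothing in the other direction, candidates start with uneven expectations.

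Everyone hears the same discussion before randomization, so it does not disturb the allocation. The expectations become arm-specific once allocation is known and can then colour self-report. The estimated AcTIVE-CBT effect is one of the quantities this pilot is run to produce. An expectation component in it cannot be separated out afterwards.

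**Working it through.** The documents give no figure that bears on this point, so the check is mainly a comparison of texts.

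**1. Does the doubt single out one arm's added content?** Section 5.3 lists three things beyond which the longer program may achieve nothing: initial education, written materials and a structure for self-directed work. A few sentences later it describes brief CBT as one psychologist session, a structured education program, written materials and independent application. The three items match the substance of brief CBT. In effect, candidates are told that extended CBT may be no better than brief CBT.

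**2. Is there a counterpart?** The description of brief CBT in Section 5.3 covers format and convenience. It does not say that one session with self-directed work may be insufficient.

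**3. Does the plan show what balance looks like?** Yes, for the procedures. Debate about LRFA is followed by an explicit statement that the steroid injections are similarly uncertain. Candidates also hear that those given the control procedure may continue to have back pain. The CBT text has no equivalent pair.

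**4. Which statements are balanced?** Section 5.3 says that all treatments are active and expected to help, and that the effective components of CBT are unknown. Both statements apply to both CBT arms.

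**5. Does the 'control' sentence break the rule in Section 5.1?** No. That rule is that participants are not told which CBT is the control. Section 5.3 discloses that one of them is, and withholds which until 3 months unless the participant asks to be unblinded sooner.

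**6. Which way could expectations push?** The doubt could lower expectations of extended CBT and shrink the contrast. Knowing that one program is a control could lower expectations of the one-session program and enlarge it. The net direction cannot be determined.

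**7. Could the pilot detect such an influence?** Assume the 20 planned completers split 10 versus 10 on the CBT factor, with a common SD. The standard error of the CBT main effect is then √(1/10 + 1/10) = √0.2 ≈ 0.45 SD. A modest expectation shift would be invisible against that.

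**The case against.** The strongest reply has four parts.

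- **The sentence is not aimed at AcTIVE-CBT alone.** It opens with CBT in general, gives AcTIVE-CBT as an example, and questions added benefit only. This stands. A reader might infer that the plan casts doubt on AcTIVE-CBT alone, or that it undoes its own rule. The neighbouring statements covering both arms rule out both readings. They do not supply the missing caution about brief CBT.
- **The 'control' sentence is consistent with Section 5.1.** This also stands. A reader might infer a contradiction, or that most candidates will guess which program is the control. The identity is withheld, and the documents do not show how many would guess. Much of any such guess would come from eight sessions versus one, which has to be disclosed.
- **The participant wording cannot be seen.** Section 5.3 describes the discussion and refers to the consent form, which is not available here. Section 5.1 says AcTIVE-CBT is called 'extended CBT' in all discussions with the patient, so the text in 5.3 cannot be verbatim. This limits the point to what the protocol says staff will explain.
- **Sampling error dominates.** With a standard error near 0.45 SD, a small shift matters little to any single estimate. That is a fair comment on scale. It does not justify leaving in an avoidable systematic influence.

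Treatment expectancy is collected at Visits 0 and 1 (Section 5.1, description of the CBT treatments) and could be described by arm. The documents do not say whether it is specific to CBT or taken before or after the consent discussion, and Section 5.6 does not use it.

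**Conclusion.** The point holds as a wording imbalance. The CBT part of the consent discussion names the longer program when raising doubt about added benefit and has no matching caution for the shorter one, whereas the procedural part states uncertainty for both treatments. This weakens neutral presentation, the main safeguard for a comparison that is unblinded and has a self-reported primary outcome. It does not cancel that safeguard or invalidate the comparison.

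No size can be put on the bias. A reader might go on to multiply the future trial's sample size by some factor. That would need an assumed expectation shift and an assumed true effect, and the documents give neither, nor the direction of the shift. No such factor should be claimed. The conclusion rests on Section 5.3 being a fair account of what candidates hear. It is worth acting on because the remedy is cheap and the effect size is a main product of the pilot.

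**What to change.** In Section 5.3 and the matching participant-facing text, replace the one-sided sentence with an even one, for example: it is not known whether extended or brief CBT works better; extended CBT offers more sessions with a psychologist, brief CBT takes less time; either could prove equal or better.

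As a secondary precaution, reword the unblinding sentence so that 'control' is not used for CBT with participants before Visit 5. It could say that at 3 months they can be told more about how the two programs were being compared.

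The cost is a consent wording change and an IRB amendment. Session numbers, time burden and voluntariness remain fully disclosed. Participants enrolled before the change will have heard the current wording, so the date of the change should be recorded.

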5.4 Inclusion/Exclusion Criteria

Initial Screening Criteria (pre-screening)				
Inclusion Criteria	Exclusion Criteria	Rationale/ Indications for Exclusion Criteria		
Chronic low back pain of duration ≥ 3 months, defined by: "How long has back pain has been an ongoing problem for you. Response of "> 3 months" defines CLBP. ⁶³ Low back pain intensity numerical rating scale (NRS) ≥ 4 (must be 4 or higher)	Clinical suspicion that the current low back pain symptoms have a significant and sustained component that is attributed to lumbar spine- related syndromes including lumbosacral radicular syndrome (radiculopathy), symptomatic lumbar spinal stenosis (neurogenic claudication), with confirmatory imaging findings, spinal instability requiring surgery, or other 'red flag' conditions (infection/ malignancy/ fracture)	Primarily due to appropriateness for the LRFA intervention vs. simulated LRFA		
Has failed at 1 st line rehabilitative treatments, including physical therapy, yoga, tai chi, chiropractic or osteopathic manipulation, and/or massage.	Pregnant females, prisoners, or the cognitively impaired (see also below)	Primarily due to appropriateness for the LRFA intervention vs. simulated LRFA		
Patient is considered as a candidate for unilateral or bilateral LRFA at 2-4 spinal levels (between L1 and S1) 'Positive responses' to 1 st set of lumbar MBBs, including 1) ≥50% pain improvement	Prior lumbar RFA Prior lumbar spine surgery involving the levels where LRFA is to be performed, within the past 2	Primarily due to appropriateness for the LRFA intervention vs. simulated LRFA		

VA Puget Sound IRB Protocol Template – Version 1.0: 04/2018

of typical low back pain, and 2) onset of typical lumbar back pain relief within 30 mins and relief lasting at least 30 mins after the onset of initial pain relief Depending on the distribution of recruited participants' MBB responses (50-79% vs. ≥80%) after the initial period of recruitment, we may restrict study participation in the participant selection phase in order to oversample participants who have ≥80% relief with MBBs.	years Lumbar fusion or instrumentation involving the levels where LRFA is to be performed Onset of the current low back pain symptoms prior to a laminectomy/discectomy/foraminotomy involving the levels where LRFA is to be performed, or within 2 years of a prior laminectomy/discectomy/foraminotomy involving the levels where LRFA is to be performed	
Must have access to a computer, tablet, or smartphone with internet access at home or at work (not via a public resource such as the public library)	Prior CBT for chronic pain (a full course focused on pain, ≥4 sessions)	Primarily due to appropriateness for the AcTIVE-CBT vs. TBSCE
Must be able to read English, provide informed consent and complete the assessment instruments accurately	Primary psychotic or major thought disorder (lifetime), any active suicidal/homicidal ideation (past 6 months), unstable or severe psychiatric/behavioral conditions (e.g. delirium, mania, psychosis)	Primarily due to appropriateness for the AcTIVE-CBT vs. TBSCE
	Hospitalization for psychiatric reasons involving psychosis other than suicidal ideation, homicidal ideation, and/or PTSD, in the past 5 years	Primarily due to appropriateness for the AcTIVE-CBT vs. TBSCE
	Cognitive limitations that would prevent participation in AcTIVE-CBT or the control behavioral intervention (score of 5/10 or less on the Short Portable Mental Status Questionnaire)	Primarily due to appropriateness for the AcTIVE-CBT vs. TBSCE
	Severe medical comorbidities posing major functional limitations in ambulation and function or medical prognosis, including vascular, pulmonary or coronary artery disease, metastatic cancer. Exclude patients with MD-diagnosed fibromyalgia or chronic widespread pain	Primarily due to general study participation Primarily due to general study participation
	Final Screening Criteria	
Must meet all of the above Initial Screening Inclusion Criteria	Must continue to meet all of the above Initial Screening Exclusion Criteria	
'Positive responses' to 2 st set of lumbar MBBs, including 1) ≥50% pain improvement		

of typical low back pain, and 2) onset of typical lumbar back pain relief within 30 mins, and relief lasting at least 30 mins after the onset of initial pain relief	
Depending on the distribution of recruited participants' MBB responses (50-79% vs. ≥80%) after the initial period of recruitment, we may restrict study participation in the participant selection phase in order to oversample participants who have ≥80% relief with MBBs.	

